The probiotic-supplemented yogurt is composed of the investigational agent, BB-12, and contains the yogurt starter culture YF-L702 (a mixed culture of *Streptococcus thermophilus* and *Lactobacillus delbrueckii* subsp. *bulgaricus*). The yogurt starter culture will be present and alive in the control yogurt. Participants are to provide informed consent at Baseline and complete a 30-day run-in period, during which they will refrain from all probiotics, and begin the antibiotic and yogurt interventions on Day 1.

Participants will be randomized to receive BB-12-supplemented yogurt or control yogurt (without BB-12), in a 2:1 (40:20 participants) allocation (**Figure 1**).

Group 1 (n=40): Probiotic, BB-12-supplemented yogurt, 4-ounces (which delivers $\geq 10^{10}$ CFU of BB-12) taken orally for 14 days and amoxicillin-clavulanate 875/125 mg, twice daily, for 7 days.

Group 2 (n=20): Control yogurt, 4-ounces taken orally for 14 days and amoxicillin-clavulanate 875/125 mg, twice daily, for 7 days.

Figure 1.

Fecal samples will be collected at home (at baseline (pre and post run-in), days 7, 14, 21 and 30) for SCFA and microbiome testing. Participants will be given detailed, written and illustrated instructions on proper sample collection procedures, and research staff will review these protocols with participants during enrollment.

Follow-up phone visits will be completed on Days 7, 14, and 30. Participants will keep a daily diary to track number, shape and consistency of bowel movements, if/when antibiotic and/or yogurt was consumed, Bristol Stool chart, general health, use of other medicines or products, adverse events, and the Gastrointestinal Symptom Rating Scale (GSRS) - Irritable Bowel Syndrome (IBS) version..

Duration: Each participant will be in the study for approximately 8 weeks total. During the first 30 days, the participant will refrain from antibiotics and probiotics (run-in period) and provide two baseline samples. The participant will be taking the antibiotic intervention for 7 days and taking the yogurt intervention for 14 days. There are two more data collection visits on day 21 and 30.

Pre run-in Baseline	Run-in (30 days)	Post run-in Day 0	Day 1	Day 7	Day 14	Day 21	Day 30
Informed Consent	No antibiotics	Fecal sample	AMC start	AMC end	Yogurt end	Fecal sample	Fecal sample
Inclusion/exclusion	No probiotics	Post-run in inclusion/exclusion	Yogurt start	GSRS-IBS	Diary end		

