9. STATISTICAL CONSIDERATIONS

9.1 General Design Issues

Primary Hypothesis: Antibiotics will result in a reduction in fecal SCFA. BB-12 supplementation will protect against antibiotic-induced SCFA (with acetate levels being used to represent the production of SCFA by gut microbiota) reduction and/or be associated with a more rapid return to baseline SCFA levels (acetate), compared to participants who receive a control yogurt without BB-12.

As reported by Hoverstad et al. (1986) and Clausen (1991), we hypothesize that antibiotic administration for 7 days will decrease mean fecal acetate levels for each participant, and that upon conclusion of antibiotic therapy fecal acetate levels will return toward baseline values for each participant.

We will compare the mean fecal acetate levels at days 7 and 30 versus the baseline values for participants receiving BB-12 or control yogurt. A significantly higher mean level of fecal acetate, calculated using one-way analysis of variance (Ganes-Howell *post hoc* test) in participants receiving BB-12 yogurt compared to the control yogurt during or after antibiotic administration, will be consistent with our hypothesis on the effect of BB-12, and will substantiate advancing the proposed study onto the next phase. As with the sample size calculation, we estimate a 42% decrease in acetate in the control/antibiotic treated group and no greater than a 15% decrease in the BB-12 treated group.

The following *biological signatures* will be assessed to determine if giving yogurt with BB-12 to humans results in a clinically meaningful change in these measures. We will move to the R33 phase if the R61 demonstrates the expected changes described for each signature, in the direction indicated:

- a. BB-12 ameliorated antibiotic-induced decreases in acetate. We expect a minimal effect size for comparison of the acetate levels in the placebo group to the BB-12-treated group to have a Cohen's $d \geq 0.6$. Effect size according to Cohen's d will be calculated at day 7 and day 30 with either day 7 or day 30 reaching Cohen's $d \geq 0.6$ constituting an achieved milestone in the R61 Phase that will justify movement to the R33 Phase. Based upon the literature, we expect a 42% decrease in acetate with antibiotics and no greater than 15% decrease in acetate with BB-12, which would yield a Cohen's $d > 0.6$.

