9.5 Outcomes

9.5.1 Primary Outcome

The primary outcome is a difference, measured at day 7, in antibiotic-induced changes in fecal SCFA (with a particular focus on acetate) in participants receiving BB-12-supplemented yogurt versus non-supplemented control yogurt.

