9.7 Data Analyses

To examine the primary hypothesis that BB-12 supplementation will protect against antibiotic-induced SCFA reduction, the mixed model will be used to analyze the treatment effect on the antibiotic-induced SCFA reduction. Statistical analyses will be performed using intent-to-treat analytic strategies. The mixed effect model will be used, which is compatible with unbalanced outcome measurements. The change of SCFA from baseline will be considered as the outcome variable of the mixed model. All time points will be included for the analysis. Covariates including age, sex, BMI and time (a continuous variable) will be adjusted when necessary. In addition, the time and treatment interaction term will be assessed by the likelihood ratio test. The random intercept will be used and the AR1 and/or compound symmetry covariance structure will be considered (and then the likelihood test can help to determine the more appropriate covariance structure). The final model selection will be performed based on information criteria such as Akaike information criterion (AIC) or Bayesian information criterion (BIC). Power: with a sample size of 40 subjects in the treatment arm and 20 subjects in the placebo arm and attrition rate of 5% at day six and 20% at day 30, we would have power of 82% to detect a moderate effect size of Cohen's $d = 0.63$ (assuming the intra-correlation correlation coefficient is 0.3). The α level of 0.05 will be used for the analysis. Since the effect size of previous study (reduction in acetate levels) is Cohen's $d = 1.23$, we should have ample power to detect the treatment effect. (The power calculation is based on the R software and packages simr, sjstats, and pwr).

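### Every covariance structure named in Section 9.7 assumes equal variance at all visits, so a day-7 contrast from the primary mixed model takes its standard error partly from the recovery visits

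*Combined protocol and SAP*

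**What the plan says.** Section 9.7 assigns the primary hypothesis to a mixed model. On the response it says: "The change of SCFA from baseline will be considered as the outcome variable of the mixed model". On the visits: "All time points will be included for the analysis". Time is listed as a continuous covariate, and the time-by-treatment interaction is to be assessed by a likelihood ratio test.

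On the covariance: "The random intercept will be used and the AR1 and/or compound symmetry covariance structure will be considered". It adds that "the likelihood test can help to determine the more appropriate covariance structure", and the next sentence leaves final model selection to AIC or BIC. No unstructured or heterogeneous-variance structure is named, and no robust standard error.

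Section 9.5.1 fixes the primary time point: "The primary outcome is a difference, measured at day 7, in antibiotic-induced changes in fecal SCFA".

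The number of SCFA visits in the model is not settled. Section 9.1 says "We will compare the mean fecal acetate levels at days 7 and 30 versus the baseline values", which gives two post-baseline visits. The Précis (Interventions and Duration) has stool collected at baseline and at "days 7, 14, 21 and 30) for SCFA and microbiome testing", which gives four.

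**The concern.** A random intercept with independent errors, compound symmetry and AR1 all imply a single variance common to every visit. Day 7 is the last day of antibiotic, and the later visits are recovery. Section 9.2 reports falls in acetate of 5% to 79% on ampicillin, and Section 9.1 expects each participant to return toward their own baseline afterwards. If that happens, change from baseline could vary less at day 30 than at day 7. The pooled variance would then understate the day-7 standard error, and the p-value and confidence interval for the primary contrast would be too optimistic. If day 7 is instead the less variable visit, because low levels leave little room to vary, the standard error is too large and power is lost. AIC or BIC can rank the named structures, but none of them lets day 7 have its own variance.

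**Working it through.** **Inputs from the plan.** Acetate SD 16 at baseline and 18 after antibiotic (9.2); intra-class correlation 0.3, allocation 40:20, attrition 5% early and 20% at day 30 (9.2 and 9.7); α = 0.05, taken as two-sided. Numbers analysed: 38:19 at day 7 and 32:16 at day 30.

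**Inputs assumed.** The documents give no day-30 SD. The first row of the table sets it to the baseline value of 16 and uses 0.3 for all correlations. The other rows set change SDs directly.

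**Plan's own figures.**
- The prior-study effect size reproduces: (45 − 24)/√((16² + 18²)/2) = 21/17.03 = 1.23.
- The plan states no standard error or error rate for the day-7 contrast. The nearest figure is 82% power at d = 0.63.
- An average over two equal-variance visits, without attrition, gives SE = √(0.65 × (1/40 + 1/20)) = 0.221, where 0.65 = (1 + 0.3)/2. Then 0.63/0.221 − 1.96 = 0.89, or 81.4% power. With the stated attrition this is about 77%; three visits with attrition give 84 to 85%.
- A day-7-only comparison at 38:19 gives 61%. The simulated model is not described, so the 82% is not called wrong here.

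**Change SDs from the plan's figures.**
- Day 7: √(16² + 18² − 2 × 0.3 × 16 × 18) = √407.2 = 20.2
- Day 30: 16 × √(2 × 0.7) = √358.4 = 18.9

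**Approximation.** With complete data, an equal-variance model estimates roughly the mean of the visit variances. The ratio of model SE to true SE at day 7 is then r = pooled SD / day-7 SD, and the actual two-sided error is about 2 × (1 − Φ(1.96 r)). The true day-7 SE with SD 20.2 is 20.18 × √(1/38 + 1/19) = 5.67.

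| Change SDs (day 7, later visits) | Pooled SD | r | Error, approximation | Error, simulated |
|---|---|---|---|---|
| 20.2, 18.9 (from the plan's figures) | √382.8 = 19.57 | 0.970 | 5.7% | 5.8% |
| 20.2, 15 (assumed) | √316.1 = 17.78 | 0.881 | 8.4% | 8.5% |
| 20.2, 12 (assumed) | √275.6 = 16.60 | 0.823 | 10.7% | 10.5% |
| 15, 20.2 (assumed) | √316.1 = 17.78 | 1.185 | 2.0% | 2.0% |
| 20.2, 15, 15, 15 (assumed, four visits) | √270.6 = 16.45 | 0.815 | 11.0% | 11.4% |

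The simulations used 20,000 trials per row at 38:19. Visit-specific variance gave 4.9 to 5.2% in every row.

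**Check with REML and the stated attrition** (2,500 trials per case). Error under the equal-variance structure, with day 7's own variance in brackets:
- plan-based SDs: 5.7% (5.2%)
- baseline-to-day-30 correlation assumed 0.7: 9.2% (5.1%)
- day-7 SD assumed to shrink with the mean, 16 × 0.58 = 9.3: 2.9% (4.6%)

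In the last case, power for the planned difference of 45 × (0.42 − 0.15) = 12.15 µmol/g is about 70%, against 78% with the correct SE.

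**Selection and identifiability** (these do not themselves change the day-7 SE):
- AR1 and compound symmetry have two parameters each and are not nested, so a likelihood-ratio test between them has 0 degrees of freedom. At two visits they are the same matrix.
- Random intercept plus compound symmetry has three parameters, of which two are identified at any number of visits.
- Random intercept plus AR1 has three parameters. Two are identified with two visits, all three with four.

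**The case against.** **The plan's own numbers show little harm.** SDs of 16 and 18 are similar, and the resulting error is under 6%. The 5% to 79% range describes on-antibiotic falls only; with no day-30 range beside it, it does not show unequal variance between visits. This stands. The larger figures are a sensitivity range, not a prediction.

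**The inflation needs a visit-specific contrast.** Section 9.7 speaks of a treatment effect with time continuous, and only assesses the interaction. For the treatment main effect averaged over two visits, simulated error stayed between 4.3% and 5.5% in every SD case (REML, compound symmetry, assumed correlation 0.5 between change scores, 3,000 trials). This also stands, but 9.5.1 makes day 7 primary, so the model has to yield a day-7 contrast and 9.7 does not define one.

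**Stronger readings a reader might infer.**
- That a likelihood test which cannot compare the candidates decides the structure. The text says only that the test can help, and AIC or BIC, which can rank non-nested models, makes the final selection. With three or more visits, random intercept against random intercept plus AR1 is also a valid nested comparison.
- That the model cannot be fitted. Compound symmetry alone or AR1 alone is estimable, and the redundant forms leave the marginal covariance, and hence the standard errors, unchanged. Random intercept plus AR1 fails only if SCFA is analysed at two visits.
- That the decision to move to R33 is compromised. The milestone in 9.1 is a Cohen's d of at least 0.6 at day 7 or day 30, a point estimate that does not use this standard error. The one-way ANOVA with Games-Howell test in 9.1 need not pool over visits either.

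Neither the milestone nor the ANOVA removes the restriction from the mixed model to which 9.7 assigns the primary hypothesis.

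**Conclusion.** The concern holds in a limited form. Every covariance structure named for the primary mixed model forces equal variance over visits, and choosing among them by AIC or BIC cannot relax this. A day-7 contrast from that model therefore has a standard error that can be too small or too large. On figures derived from the plan the error rate is about 5.5 to 6%, which is minor. It is about 8 to 10% if the day-30 change SD is 15 or 12, and about 2% if the SDs are 15 at day 7 and 20.2 at day 30. Those values are assumed because no day-30 SD is given, and all of the error rates suppose that a visit-specific day-7 contrast is taken from the model. The nesting and redundancy points are faults of specification that do not change the standard error. This is a worthwhile low-cost correction, not a fatal flaw.

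**What to change.** In Section 9.7:

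1. Treat visit as a factor with visit-by-treatment terms kept in the model, and state that the primary result is the day-7 treatment contrast.
2. State which post-baseline SCFA visits enter the model.
3. Pre-specify one unstructured covariance over those visits, with Kenward-Roger degrees of freedom.
4. Name a heterogeneous-variance structure, such as heterogeneous compound symmetry, as the fallback for non-convergence.
5. Delete the likelihood-test choice between AR1 and compound symmetry.

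The cost is a few lines of text and no new data. The covariance has 3 parameters for two visits or 10 for four, against 2 for compound symmetry or AR1, with slightly fewer error degrees of freedom. About 57 participants at day 7 can support that.

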9.8 Missing Data

We understand the importance of limiting missing data and as in previous studies the PI and project coordinator will work very closely to prevent missing data. However, there will be some missing data, which we anticipate will be missing at random (MAR). Although it is challenging to test the assumption MAR versus missing not at random (random) due to incomplete information for such test (122), we will carefully examine the missing patterns and perform sensitivity analysis for the MAR assumption (123). The multiple imputation will be used to deal with the missing data (e.g. the missing covariate and baseline outcome variable).

A sensitivity analysis could be used to explore the impact of departures from the MAR assumption underlying the main analysis. For example, we let the mean of observed data and the mean of the unobserved data differ from each other, adjusted for other observed variables. Under an MAR analysis, *the difference* is assumed to be zero. We then evaluate the impact of difference on treatment effect inference under MAR assumption.

To test the secondary hypothesis, we will examine the treatment effects on multiple microbiota composition scores, for example, Bray-Curtis similarity score, Chao1 metric (α -diversity or richness), the Shannon index. We will apply mixed model to analyze these metrics and then perform multiple testing adjustment using FDR and/or FWER correction. The secondary hypothesis analysis is primarily exploratory and will not be used for Go/No Go for R33.

10. DATA COLLECTION AND QUALITY ASSURANCE

10.1 Data Collection Forms

Blinded research assistants will be collecting participant information in person or over the phone, and will be responsible for picking up samples from participants. All investigators and research personnel will take required classes on human subject research and the protection of individually identifiable health information prior to any contact with the participants.

Participants will be completing questionnaires with protected health information, and the release of confidential information is a risk. The research staff will take all necessary precautions to minimize this risk. Participants' addresses and phone numbers will be collected, as will other private health information. In accordance with the appropriate HIPAA regulations, all information will be protected and kept confidential at all times. All contact and study information will be kept on password-protected computers or online databases, participants will be identified by code, and no information will be released without proper approvals or permissions.

10.2 Data Management

Data management is a joint effort between the study team, PIs, and biostatistician. The investigators are responsible for ensuring the accuracy, completeness, legibility, and timeliness of the data reported. All source documents and data should be should be attributable, legible, contemporaneous, original, accurate and complete (ALCOAC). The investigators will maintain adequate case histories of study participants, including accurate case report forms (CRFs), and source documentation.

10.2.1 Data Collection

Data collection and accurate documentation are the responsibility of the study staff under the supervision of the investigator. All source documents and laboratory reports are maintained by the study team, who will ensure that they are accurate and complete. Unanticipated problems and adverse events must be reviewed by the investigator or designee.

10.2.2 Data Management System

This study uses a project database within the Remote Electronic Data Capture (REDCap) system hosted by MedStar Health Research Institute (MHRI), and is FDA 21 CFR Part 11 compliant. The database will be secured with individual account logins and password protection. Each user must use their unique, assigned user account and password.

The database incorporates an electronic audit trail to show change(s) to data after original entry including the date/time and user making the change. REDCap has some builtin validation processes to ensure data quality, including minimum/maximum ranges, data type, calculations, date, and branching logic fields.

The data entry system is designed to allow information contained on a single form to be entered over one or multiple keying sessions. For direct electronic capture, it is recommended to enter any one form in its entirety rather than breaking up a single form into multiple keying sessions. Once an entry is created, any later additions or changes to incomplete forms or sessions will require the user to log a 'change reason'. The data collection forms were also designed for keying directly into the data entry system without the need for additional transcription.

Entries in REDCap may be saved locally on the device and then backed up on the server once the device is online. In the case of an outage of the REDCap system, a backup paper form will be used to collect the data, and will be entered into the database at a later time.

The biostatistician will receive only coded information that is entered into the database under study identification numbers. Electronic communication with outside collaborators will involve only de-identified information.

10.2.3 Source Documentation

Source documents are original documents, data, and records (e.g., hospital records, clinical and office charts, laboratory reports, memoranda, diaries or evaluation checklists, or pharmacy dispensing records) which first records a finding, observation, or other activity during a study.

Since this study will enroll generally healthy participants and data are entered directly into the electronic database, the case report and data collection forms will serve as the source documents. Any hardcopy participant study records, such as case report forms, medical records (if applicable), and participant files, are kept in a locked cabinet inside a locked office. Electronic records, identified by study ID code only, are stored in the REDCap database or on Georgetown University secure servers, both of which require a username and password. Only authorized, trained research staff will have access to the data.

Source Document/Form	Abbreviation	Key Form	Completed by
Baseline Health Status	BH	X	Research staff
Daily Assessment Diary (Days 1-7, 8-14)	DD	X	Participant
Demographic Information	DI	X	Research staff
Automated Self-Administered 24-Hour (ASA24®) Dietary Assessment Tool	ASA24		Research staff
Follow-up Form	FU	X	Research staff
Gastrointestinal Symptom Rating Scale - IBS	GS		Research staff
Inclusion/Exclusion	IE		Research staff
Informed Consent Process Documentation	IP		Research staff
Post Run-In Health Status	PR	X	Research staff
Pre-Screening	PS		Research staff
Randomization	RZ		Research staff
Sample Collection	SC		Research staff
Event-driven forms			
Adverse Event Report	AE	X	Research staff
Diarrhea Report and Follow-up	DR		Research staff
Missed Contact Report	MC		Research staff
Serious Adverse Event Report	SA	X	Research staff
Withdrawal from Intervention	WI		Research staff

Other source documents may include study progress notes, electronic or paper medical records, laboratory reports, memoranda, diaries, and other records pertaining to the participant while in the research study.

10.2.4 Study Records Retention

Study documents will be retained for a minimum of 3 years following the formal discontinuation of clinical development of the investigational product, unless the funder specifically requests otherwise.

10.3 Quality Assurance

10.3.1 Training

All study staff will complete training on appropriate data collection and entry procedures, as well as the study specific databases. Completed trainings will be recorded in the training log, which is on file in the study regulatory binder. All key personnel (all individuals responsible for the design and conduct of this study) have completed Human Subjects Research Protection Training.

10.3.2 Quality Control

The PI of the recruitment site, [name], is responsible for quality management for this study. The Project Coordinator has been designated by [name] to be responsible for the implementation of the quality management plan.

All source documents and case report forms are to be completed in a manner to ensure the data is attributable, legible, contemporaneous, original, accurate and complete. ALCOAC applies to both paper and electronic source data, and the records that hold that data. The REDCap system uses an electronic audit trial and signature capability to ensure each addition or change in the database is attributable to a unique user, when it was added/changed, the reason for the change, and when the review of the record is completed.

